The two largest randomized controlled trials of yoga for civilian PTSD suggest that the practice leads to meaningful change in PTSD symptoms from pre- to post-treatment; in both cases this effect was greater than the control condition with effect sizes in the range of 1.07-1.65 (Jindani, Turner, & Khalsa, 2015; van der Kolk et al., 2014). Although these two trials suggest optimism, the broader literature on yoga for PTSD is highly variable and of inconsistent quality, thus limiting the conclusions that can be drawn. Several studies show no difference between yoga and a control condition (e.g., Mitchell et al., 2014; Thordardottir, Gudmundsdottir, Zoega, Valdimarsdottir, & Gudmundsdottir, 2014), and one very small study found negligible effect on PTSD symptoms among Veterans (Staples, Hamilton, & Uddo, 2013). Whereas methodology may be one factor in the variability in outcomes observed in yoga studies, another likely source is the fact that yoga practice varies widely, ranging from quite vigorous to highly relaxing and including no to heavy emphasis on physical asanas (postures), meditative practices, spirituality or breath control. *Just as trying to establish whether or not "psychotherapy" is effective for PTSD would be untenable because of the broad range of procedures encompassed by that term, it is unlikely that "yoga" will be proven efficacious or not. The quest for effective psychotherapeutic strategies was driven by a conceptual understanding of processes that create or maintain psychopathology and the use of techniques to modify those mechanisms. Similarly, we suggest that delivering efficacious yoga-based interventions will depend on understanding mechanisms of change and targeting those variables in the therapeutic teaching of yoga.*

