Tolerance of discomfort has been described in multiple ways in the literature and has been associated with PTSD. The term “distress tolerance” is used to describe the ability to tolerate uncomfortable emotions (Simons & Gaher, 2005). Distress tolerance inversely correlates with PTSD severity; specifically, those with poorer distress tolerance have more re-experiencing symptoms and emotional numbing (Vujanovic et al., 2013). The idea that increased tolerance of discomfort may ameliorate PTSD is supported by studies of “anxiety sensitivity (AS),” which is the fear of anxiety symptoms (physiological, cognitive and social). AS is not only related to the development and maintenance of the PTSD ([name], Kennedy, & Stein, 2002), but change in AS predicts change in PTSD symptoms. Further, interventional studies show that reducing AS ameliorates PTSD (Allan, Short, Albanese, Keough, & Schmidt, 2015). Further, Medina et al. (2015) showed that hatha yoga increased distress tolerance (specifically an aspect of distress tolerance called distress absorption), which led to more adaptive coping (namely less emotionally-driven eating in response to stress). A direct extension of these data is a multiple mediation model for PTSD involving tolerance of discomfort and coping, as diagrammed in Figure 2. We will examine the model that yoga increases tolerance of discomfort, which improves coping, which in turn reduces PTSD symptoms. We will compare the fit of this model to the models including each of the mediators alone. To inform future work, we additionally will explore whether any combination of the Attention and Coping Models explains more variance than either one alone.

Summary. In light of the evidence presented, we predict that yoga will be associated with clinically significant change in PTSD symptoms and that the change associated with yoga will be significantly greater than the change associated with physical activity because of the meditative nature of the practice. We will secondarily assess the impact of the two interventions on symptoms that are commonly associated with PTSD and examine the clinical utility of both interventions (Smart, 2006) with the ultimate goal of guiding the clinical application of the practice. Further, we have described two models that link yoga practice to change in PTSD symptoms. The fit of the proposed Attention and Coping Models will be assessed and compared.

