Innovation. The present study extends and compliments previous yoga research. Much of the current yoga literature is limited by small sample sizes and poor methodological rigor. In response to this need, the proposed study includes a randomized controlled design, with an active control condition that is matched for time/attention, social group interactions, attention, and expectancy. It features standardized and psychometrically sound assessment instruments, including blinded evaluation, and addresses the limited generalizability of previous samples by including both men and women with broad inclusion/exclusion criteria. Finally, it is set in a Veteran population, which is an understudied group in the published literature and may differ in important ways from non-military populations. Furthermore, the yoga intervention is a manualized Hatha yoga, which has been implemented in prior studies at this facility, and is reviewed for fidelity. Thus, the proposed project addresses an important need for high quality studies of yoga for PTSD. *The greatest innovation, however, lies in the evaluation and comparison of the Attention and Coping Models. Examination of these mechanisms will advance our understanding of the way in which a guided asana practice may impact PTSD, but will also inform yoga-based mental health treatment more broadly as these transdiagnostic processes are applicable to other mental health concerns.*

Research Design and Methods

The proposed study is a randomized controlled trial of Hatha yoga as compared to supportive physical activity in Veterans with PTSD. A sample of approximately 96 recruited (refer to Sample Size). Longitudinal outcome assessment will take place over approximately a 6 month period; refer to Table 1 for an overview of measures at each time point. A 3-month follow-up is planned because information about maintenance of change following the completion of a yoga intervention is important given the long-term follow-up data from the van der Kolk trial, which suggest that ongoing practice is critical continued clinical effects (Rhodes, Spinazzola, & van der Kolk, 2016).

Procedures

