Each outcome variable will be graphed versus time for each subject for all available time points (baseline, mid-treatment, post-treatment, follow-up) to evaluate what function of time best describes the data. Hypotheses 1a and 1b will be tested using the Mixed Effect Model (Hedeker, Gibbons, & Waternaux, 1999). This method is robust with respect to drop-out and missing data. These mixed models allow us to assess whether important estimates are dependent on missing data patterns, and provide overall estimates of effects by averaging over the various missing-data patterns (Hedeker et al., 1999). In addition, we will use the extension of the Pattern-Mixture Models (Guo, Ratcliffe and Ten Have, 2004), which allows subject-to-subject heterogeneity and assess if there is bias due to drop out or missing data. The Mixed Effect method has several advantages over more traditional analytic approaches such as a change score, end-point or repeated measures analysis of variance. It allows the inclusion of subjects with missing data or those who were terminated early in the study, without relying on data imputation procedures. This method provides an estimate of the individual variability around the population trend, the variability of the individual intercepts (baseline values) and slopes (changes across time), and the correlation between them. We will include a random intercept, a random effect for assessment time, and fixed effects for comparison groups and group-by-time interaction in the model. A fully saturated treatment by time model will be utilized for inference. Co-variance structure will be chosen based on Akaike's Information Criterion (AIC). Random group level treatment effects will also be evaluated for importance based on the model AIC. This allows for any group level effects to be incorporated into the model. Denominator degrees of freedom will be calculated using the Kenward-Roger small sample correction. Statistical significance will be determined by $p < .05$ for hypothesis 1a and $p < .01$ (.05/5 to correct for multiple comparisons) for hypothesis 1b.

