Sample size. We used the method provided by Hedeker, Gibbons, & Waternaux (1999) for the Random Regression Model and the RMASS program provided by Hedeker (2016) to estimate needed sample size for Aim 1. Medium effect size was selected based on finding from previous yoga trials (Wells et al., 2016) and was defined as a between-group difference increasing linearly from 0 at baseline to .5 SD units at the last time point. The minimum power estimation is based on sample size calculation for 10% and 20% attrition, correlations of 0.2, 0.5, and 0.8 between the repeated measures, and for medium and large effect sizes. We are confident that with the proposed total sample size of at least 48/arm would be sufficient to achieve a minimum 80% power for the primary aim.

Management

Management of this single-site study will be [name] responsibility. She has considerable experience in research management from small developmental grants (e.g., NCCIH R34) to a large multi-site consortium (INTRuST PTSD/TBI Clinical Consortium Deputy Director) and center of excellence (VASDHS CESAMH Associate Director). Administrative aspects of the project will be supported by [name], who has been [name] lead coordinator for more than a decade. [name] will coordinate scientific aspects of the project, holding regular meetings with the investigative team. [name], the study biostatistician, will work closely with [name] around data management and analysis. [name] will draw on his experience with yoga research to help with issues of recruitment, enrollment and retention. Drs. [name] (attention) and [name] (pain) will provide guidance in their relative areas of expertise. [name], who is a licensed clinical psychologist, also will be responsible for clinical oversight. The timeline of major study activities is presented in Table 2.

Table 2. Study Timeline

Year 1 (2018-2019)	Year 2 (2019-2020)	Year 3 (2020-2021)	Year 4 (2021-2022)	Year 5 (2022-2023)
Original Timeline				

Set-up	Recruitment (approx. 6/month x 30 mos)	Follow-up, data lock	Dissemination	Analyses	
Regulatory	Assessment				
Hiring	Intervention delivery, fidelity (12 groups)				
Training	Data management				
Recruitment	DSMB reporting				
Revised Timeline					

 ✓ Set-up ✓ Regulatory 	
 Recruitment (approx. 6/month x 30 mos) Assessment Intervention delivery, fidelity (12 groups) Data management DSMB reporting 	Follow-up, data lock	Dissemination	Analyses	

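### The minimum 80% power claim fails for the plan's own medium effect at correlations 0.2 and 0.5, and no contrast or visit is named to decide hypothesis 1a

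*Combined protocol and SAP*

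**What the plan says.** The Analytic Plan tests hypothesis 1a in a mixed model with a random intercept, a random time effect and "fixed effects for comparison groups and group-by-time interaction in the model". It adds: "A fully saturated treatment by time model will be utilized for inference". Significance for 1a is p < .05, and all tests are two-tailed. CAPS total is the primary clinical measure (Assessment, Clinical outcomes). Table 1 schedules it at baseline, post-treatment and follow-up, not at mid-treatment. No baseline constraint or baseline covariate is planned for CAPS.

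The Sample size paragraph defines the medium effect as a difference between arms "increasing linearly from 0 at baseline to .5 SD units at the last time point". It refers to a "sample size calculation for 10% and 20% attrition", three correlations between repeated measures (0.2, 0.5, 0.8) and both medium and large effects. It concludes that at least 48 per arm is "sufficient to achieve a minimum 80% power for the primary aim". No result is shown for any single scenario.

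The wording of hypothesis 1a does not appear in the document. The nearest statement, in the Background summary, is that "the change associated with yoga will be significantly greater than the change associated with physical activity", and it names no visit.

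**The concern.** A minimum over a set of scenarios must hold in the worst of them, and that set includes the 0.5 SD effect at r = 0.2 with 20% attrition. With 48 per arm and a contrast on change from baseline, 80% looks out of reach there. The stated power is what readers would use to interpret a null result, in a trial cut from a target of 144 completers to about 96 enrolled.

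Second, a saturated model with two post-baseline CAPS visits yields several tests of the treatment effect: a contrast at post-treatment, a contrast at follow-up, and a joint test on 2 degrees of freedom. The plan does not say which of them decides 1a. This matters for the false-positive rate if the choice stays open until results are seen. It also matters for power, because the best test depends on when the effect appears.

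Third, leaving the baseline mean free in each arm is valid, but it spends precision that the baseline CAPS data could recover.

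**Working it through.** **Inputs from the document.** 48 per arm; two-sided .05; three CAPS visits, about equally spaced (follow-up is 12 weeks after the final class); effect 0, 0.25 and 0.5 SD at the three visits; r = 0.2, 0.5, 0.8; attrition 10% and 20%.

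**Assumptions.** Compound symmetry, normal approximation, attrition cumulative to follow-up, and a large effect of 0.8 SD (the document gives no value).

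**Step 1: the plan's figure, medium effect.** With baseline free by arm, the last-visit contrast is a difference in change. In SD units its standard error is √(2 × 2(1−r)/n), and power is Φ(0.5/SE − 1.96).

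- r = 0.2: SE = √(3.2/48) = 0.258, z = 1.94, power 49%
- r = 0.5: SE = √(2/48) = 0.204, z = 2.45, power 69%
- r = 0.8: SE = √(0.8/48) = 0.129, z = 3.87, power 97%

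| Attrition | n per arm | r = 0.2 | r = 0.5 | r = 0.8 |
|---|---|---|---|---|
| 0% | 48 | 49% | 69% | 97% |
| 10% | 43.2 | 45% | 64% | 96% |
| 20% | 38.4 | 41% | 59% | 93% |

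The 80% is not reproduced at r = 0.2 or 0.5. Reaching it with complete data needs about 62.8 × 2(1−r) per arm, where 62.8 = 2 × (1.96 + 0.84)²/0.5². That is 101 per arm at r = 0.2 and 63 at r = 0.5.

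**Step 2: other tests and other assumptions.**

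- *Linear slope over three equally spaced visits.* Its weights are proportional to (−1, 0, 1), so it is the same contrast with complete data: 49/69/97%.
- *Joint 2-df test.* The noncentrality is z² = 3.75, 6.0 and 15.0, giving 39/58/94%.
- *Slope with a fourth visit.* CAPS is not measured then; even so, power is only 53% and 73% at r = 0.2 and 0.5.
- *Post-treatment contrast.* The linear build-up leaves 0.25 SD there, so power is 23% at r = 0.5.
- *AR(1) instead of compound symmetry.* 52% at r = 0.5. At r = 0.8 it is 82% with complete data and 76% at 20% attrition.
- *Effect of 0.8 SD.* 87% at r = 0.2 with complete data and 79% at 20% attrition; at least 94% at r = 0.5.

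**Step 3: retention.** The Acceptability section reports 80% retention at 12 weeks and 73% at 6 months in the site's back-pain trial of this yoga protocol. Follow-up here falls 12–14 + 12 = 24–26 weeks after the start. At that retention and r = 0.5 the plan as written has about 56% power.

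**Step 4: false positives.** Under compound symmetry the post-treatment and follow-up change contrasts correlate 0.5. In 2,000,000 null draws at .05 each, at least one of the two visits is significant in 9.1%. Adding the joint test gives 9.9%.

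**Step 5: baseline adjustment.** The variance factor falls from 2(1−r) to 1−r². Without a phase term, complete-data power is 70% at r = 0.2 (z = 2.50), about 80% at r = 0.5 (z = 2.83) and 98% at r = 0.8.

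Allocation moved from 2:1 to 1:3, so phase is associated with arm. Assume n₁ + n₂ = 96 and (2/3)n₁ + (1/4)n₂ = 48, which gives 57.6 and 38.4. The second phase is then 20% of the yoga arm and 60% of the control arm. A stable 0.3 SD phase difference (assumed) does not bias the written change contrast. It does bias a common-baseline model without phase, by 0.3 × 0.4 × (1 − 0.5) = 0.06 SD at r = 0.5. Power at r = 0.5 with phase included:

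| Model | 0% | 10% | 20% | Gain over plan |
|---|---|---|---|---|
| Plan as written | 69% | 64% | 59% | – |
| Common baseline, phase main effect | 79% | 75% | 70% | 10–11 points |
| Baseline covariate, phase main effect | 76% | 71% | 66% | 7 points |
| Common baseline, phase by visit | 73% | 69% | 64% | 4–5 points |

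At r = 0.8 with complete data, the common-baseline model gains about 1 point with a phase main effect and loses about 1 with phase by visit.

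**The case against.** **The plan does name a test framework.** This is right. It gives the model, the group-by-time term, a small-sample correction and a single .05 for 1a. Only the deciding contrast and its visit are missing. Nor is a last-visit contrast planned: the last time point appears only in the definition of the effect size. The power result survives this, because the slope and the joint test also miss 80% at r = 0.2 and 0.5.

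**The plan promises to adjust p-values as appropriate.** That sentence closes the Analytic Plan's main text and bears on this point. But it names no family of tests and no method, so it does not settle which test decides 1a.

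**The trial was sized for something larger.** The Pilot Effect Sizes section speaks of medium to large effects, and 0.8 SD roughly rescues the claim. But the Sample size paragraph defines the medium effect in figures and then states a minimum.

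**Evidence of conflict over the visit is thin.** A reader might set "A 3-month follow-up is planned because information about maintenance of change following the completion of a yoga intervention is important" against the last-time-point definition and see a contradiction. The former is a reason for having a follow-up, not a rival primary test. Likewise "the practice leads to meaningful change in PTSD symptoms from pre- to post-treatment" describes other trials.

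**The retention comparison is indirect.** The back-pain trial offered 24 classes and compared immediate with delayed yoga; here there are 12 classes and an active control. The document also does not say whether attrition is cumulative. If 20% were per interval, retention at follow-up would be 0.8 × 0.8 = 64%, below 73%, and power would be lower than shown. So it cannot be said that the plan's attrition range is too favourable; 73% is a useful extra scenario.

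**Conclusion.** The claim of at least 80% power is wrong over the plan's own scenarios. For the 0.5 SD effect it is about 49–69% with complete data and 41–59% at 20% attrition for r = 0.2–0.5. This rests on compound symmetry; AR(1) gives lower power for the plan as written. The claim is roughly met at r = 0.8 under compound symmetry, or for an assumed 0.8 SD effect.

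The deciding contrast and visit for 1a are not stated in the document. If hypothesis 1a itself names a visit, that gap shrinks to carrying the visit into the Analytic Plan and the Sample size paragraph.

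Three stronger readings are tempting, and the document does not support them. First, that the trial runs a 10% type I error: the 9–10% arises only if success is claimed on any of the readings without correction, and any one test named in advance holds 5%. Second, that the free baseline biases the comparison: on this point the written model is valid and only less efficient. Third, that adjustment restores 80% power: it does so only at about r = 0.5 with complete data and no phase term.

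**What to change.** Before outcomes are compared by arm:

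1. Restate the power for the medium effect under the chosen test, scenario by scenario, say whether attrition is cumulative, and add a row at 73% six-month retention.
2. Name one contrast or joint test on CAPS that decides 1a, name its visit, and state the effect assumed there. The choice is the sponsor's. It matters: with baseline adjustment (no phase term), r = 0.5 and complete data, an effect building to 0.5 SD gives 29% power at post-treatment, 81% at follow-up and 73% jointly. An effect of 0.5 SD at post-treatment that halves by follow-up (assumed) gives 81%, 29% and 73%.
3. Fit a common baseline mean across arms, or use baseline CAPS as a covariate with baseline removed from the response. Include a term for allocation phase and state whether it enters as a main effect or by visit. If a 0.3 SD phase difference arose only by follow-up (assumed), the written contrast would itself be off by 0.3 × 0.4 = 0.12 SD, and only phase by visit removes that.

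The cost is SAP wording and a small code change, with no new data. The stated power becomes less favourable, the freedom to pick a test later is given up, and at r near 0.8 the adjustment brings almost nothing or loses about a point.

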Clinical outcomes. The **Clinician Administered PTSD Scale (CAPS-5)**; Weathers, Blake, et al., 2013) will be used to establish the PTSD diagnosis and quantify severity. This clinician-rated measure of PTSD is the “gold standard” for assessing PTSD and takes 45-60 minutes to complete. The CAPS has high internal consistency (for the DSM-IV version, alphas of 0.87 and 0.88 for the three PTSD symptom clusters and 0.95 for PTSD symptoms overall) and validity (sensitivity, specificity, efficiency, and agreement). The CAPS total score will be used as the primary measure of clinical outcome. Given our interest in exploring the effect of these interventions on symptoms that commonly co-occur with PTSD, we will also assess depression severity as measured by the 20-item **Center for Epidemiologic Studies Depression Scale Revised (CESD-R)**; Eaton, Muntaner, Smith, Tien, & Ybarra, 2004), general anxiety as measured by the 40-item **State-Trait Anxiety Inventory (STAI)**; Spielberger, Gorsuch, Lushene, Vagg, & Jacobs, 1983), anger as measured by the 35-item **State-Trait Anger Expression Inventory – II (STAXI-II)**; Spielberger, 1991) and sleep problems as measured by the 7-item **Insomnia Severity Index (ISI)**; Bastien, Vallieres, & Morin, 2001), a 7-item instrument that assesses the consequences of and distress related to insomnia, will be included as well. Finally, the **Sheehan Disability Scale (SDS)**; Sheehan, Harnett-Sheehan, & Raj, 1996), a 3-item measure of impairment in work, social and family settings, will be included. This widely-used but low-burden measure of disability has been shown to change with treatment in similar population samples (e.g., [name], Schnurr, et al., 2016).

Clinical utility. Clinical utility can be defined as the usefulness of an intervention in clinical practice and is considered to have four major dimensions (Smart, 2006). The **appropriateness** of yoga for PTSD depends on its efficacy (addressed in Aim 1) but also on the successful integration of the intervention into current care practices. **Accessibility** involves the factors involved in making yoga available to Veterans. Issues such as the usability of the manual and the way in which training can be conducted speak to **practicality**. Finally, the **acceptability** of yoga depends on its reception by key stakeholders, including Veterans and clinicians. Aspects

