remove variables or create composites. Correlation coefficients among the outcomes for each mediator will be examined. Furthermore, the main effect of each outcome will be examined in the mixed effect model. Low correlated outcomes or outcomes that are highly (greater than .8) correlated with each other and/or low contribution in the model will be considered to be dropped from the model. The effect of mediators in the model can be calculated based on either the difference between two regression parameters ($\tau - \tau^2$) or the multiplication of two regression parameters ($\alpha\beta$) (MacKinnon, Warsi, & Dwyer, 1995). The variance estimates produced by the various methods are quite similar to each other and to the true value of the variance in situations involving continuous multivariate normal data and a continuous independent variable (MacKinnon et al., 1995). Although there is some evidence that the least model in the case-control study design setting this approach could provide biased estimations for the indirect effects (Wang et al., 2012), we believe the Sobel (1982) procedure to test for significant mediation is most appropriate approach for this study. Next we will use the formula provided by MacKinnon and Dwyer (1993) to determine the percentage of the intervention condition to primary outcome path that was accounted for by change in our mediator. We acknowledge that this method may not be supportable given the need to reduce sample size. If the study biostatistician determines that this is the case, she will utilize other strategies to analyze available data and generate testable hypotheses for future studies. The exploratory aim will be analyzed using similar approach. Data will be analyzed from all randomized subjects on whom we have a baseline assessment and at least one post-baseline evaluation. All statistical tests will be two-tailed. We will adjust p-values for multiple testing as appropriate.

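### Hypothesis 1b tests five secondary outcomes by single-step Bonferroni; this is valid, but Holm's step-down keeps the same 5% familywise limit and is never less powerful, with a gain that depends on how many outcomes respond

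*Combined protocol and SAP*

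**What the plan says.** The Analytic Plan tests hypotheses 1a and 1b with a mixed-effects model. For the primary outcome, "Statistical significance will be determined by $p < .05$ for hypothesis 1a". For 1b the threshold is p < .01, with the reason given as "05/5 to correct for multiple comparisons) for hypothesis 1b". Later in the same section come two general statements: "All statistical tests will be two-tailed" and "We will adjust p-values for multiple testing as appropriate". No step-down or other sequential procedure is named anywhere.

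The five outcomes can be identified. Under Clinical outcomes the plan says "we will also assess depression severity as measured by the 20-item" CESD-R, then adds anxiety (STAI), anger (STAXI-II), insomnia (ISI) and disability (SDS). Table 1 marks the same five instruments as Aim 1b.

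The Sample size section defines a medium effect as a "between-group difference increasing linearly from 0 at baseline to .5 SD units at the last time point". It considers "10% and 20% attrition, correlations of 0.2, 0.5, and 0.8 between the repeated measures", and concludes that "at least 48/arm would be sufficient to achieve a minimum 80% power for the primary aim". It gives no effect size, power or between-outcome correlation for 1b.

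**The concern.** Under the stated rule each 1b outcome is compared with .01 whatever the other four show. Holm's procedure orders the five p-values and compares them in turn with .05/5, .05/4, .05/3, .05/2 and .05, stopping at the first that fails. Its first step is the Bonferroni step and every later threshold is looser, so nothing that Bonferroni declares significant is lost.

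What is at stake is secondary power. The Feasibility section reports that the target fell from 144 completers to about 96 enrolled, and power is claimed only for the primary aim. The Background says the secondary symptoms are assessed to help guide clinical use of yoga, so it matters which of the five are declared different, not only whether one is.

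**Working it through.** **The plan's figure.** .05/5 = .01, which reproduces exactly. With five independent true nulls the familywise error is 1 − (1 − .01)^5 = 4.9%.

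**Inputs from the documents.** Five tests, two-sided; 48 per arm; 0.5 SD; 20% attrition, giving 0.8 × 48 = 38.4 per arm; repeated-measure correlation r = 0.2, 0.5 or 0.8.

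**Assumptions not in the documents.** The same 0.5 SD applies to every affected 1b outcome; between one and five outcomes are truly affected; the between-outcome correlation lies anywhere from 0 to 0.8.

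**Power per outcome under Bonferroni.** For a comparison of change from baseline, z = 0.5 / √(2(1 − r) × 2/n), and power at .01 is about Φ(z − 2.576).

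- r = 0.5, n = 48: z = 0.5/√(2/48) = 2.45; power Φ(−0.13) = 45% (at .05 it would be 69%).
- r = 0.5, n = 38.4: z = 0.5/√(2/38.4) = 2.19; power Φ(−0.39) = 35%.
- r = 0.8, n = 48: z = 0.5/√(0.8/48) = 3.87; power Φ(1.29) = 90%.

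**Bonferroni against Holm.** Five equicorrelated z-statistics were simulated, 150,000 to 400,000 draws per scenario. Mean power per outcome, all five affected:

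| Setting | Bonferroni | Holm |
|---|---|---|
| 48/arm, r = 0.5 | 45% | 53–54% |
| 38.4/arm, r = 0.5 | 35% | 41–42% |
| 48/arm, r = 0.8 (between-outcome correlation 0 to 0.7) | 90% | 95–97% |

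Gain by number of outcomes truly affected (48/arm, r = 0.5):

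| Affected | Gain, percentage points |
|---|---|
| 5 | 8.2–8.9 |
| 4 | about 5.5 |
| 3 | about 3.2 |
| 2 | about 1.5 |
| 1 | about 0.1 |

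**Cross-check.** A linear-trend contrast over four visits, with compound symmetry and 10–20% attrition, comes closer to the plan's power method. At 0.5 SD with all five affected, the gain is 3.8–6.4 points at r = 0.2, 8.2–9.3 at r = 0.5 and 3.6–7.1 at r = 0.8. With four affected it is 2.4–5.8 across that grid. At 0.8 SD with all five affected it ranges from 0, where power is already near 100%, to 12.

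**Error control.** With all five nulls true the two procedures have identical familywise error, because both first compare the smallest p-value with .01. It is 4.9% at between-outcome correlation 0, about 4.2% at 0.5 and 3.0% at 0.8. When some outcomes are truly affected, Holm uses more of the 5% allowance than Bonferroni but stays within it: with four affected (48/arm, r = 0.5, between-outcome correlation 0.5) the error on the fifth is 2.7%, against 1% for Bonferroni.

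**At least one rejection.** For the same reason, the chance of at least one significant 1b result is the same under both rules. In no draw did Bonferroni reject an outcome that Holm did not.

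**The case against.** The strongest defence is that nothing here is wrong. Bonferroni is valid, prespecified and simple, and 99% intervals match it directly. Holm has no equally simple matching intervals. The plan describes these outcomes as an exploration of symptoms that accompany PTSD, and hypothesis 1a at .05 is untouched. All of this stands, and it is why the point is optional.

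It could also be said that the closing promise to adjust p-values where appropriate leaves room for Holm. It names no procedure and does not displace the explicit .01 rule for 1b.

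Three stronger readings are tempting, and the documents do not support them.

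- A reader might infer a fixed loss of 7 to 9 points per outcome. That needs all five outcomes to shift by 0.5 SD with r near 0.5. The plan's own review of pilot effect sizes reports that the largest randomised yoga trial for PTSD improved insomnia and anxiety but not depression, and that was against a wait list. Here the comparator is active, so fewer than five real effects is plausible.
- A reader might infer that Holm helps most because these symptoms move together. In most settings the gain is flat or falls as the between-outcome correlation rises: at z = 3.87 it is about 6.5 points at correlation 0 and 4.5 at 0.7. What drives the gain is how many effects are real.
- A reader might infer a type I error problem. There is none under either rule.

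**Conclusion.** The point holds as an avoidable inefficiency. That Holm controls the same 5% familywise error and never rejects less is a general result that needs no assumption about effect or correlation. The size of the benefit is conditional. At 0.5 SD, 48 per arm and r = 0.5 it is at most about 9 percentage points of mean power per outcome, reached only if all five outcomes respond; it shrinks to nothing if only one does. Neither the number of responding outcomes nor their correlation can be taken from the documents. The primary analysis and the chance of finding any secondary effect are unaffected. It is a cheap improvement and an optional refinement.

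**What to change.** In the Analytic Plan, replace the p < .01 (.05/5) rule with: *Holm step-down across the five 1b tests at familywise .05, two-sided.* Report Holm-adjusted p-values beside 95% intervals labelled as unadjusted for multiplicity. Make the change before outcome data are examined by arm.

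The cost is one sentence, with no extra participants or visits and the same 5% familywise limit. The one drawback is that an unadjusted 95% interval may exclude zero for an outcome that Holm does not reject; the label on the intervals should say so. If matching intervals matter more to the investigators than the extra power, keeping Bonferroni is defensible, and the plan should state that reason.
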